In July 2012 the Joint Committee on Vaccination and Immunisation (JCVI) proposed an extended annual influenza immunisation programme for children 2 -17 years old using egg-containing LAIV (https://www.gov.uk/government/uploads/system/uploads/attachment_data/file/224775/JCVI-statement-on-the-annual-influenza-vaccination-programme-25-July-2012.pdf). Contraindications to the administration of LAIV will cause disruption to the roll out of the new vaccine programme and require primary and secondary care resources for the immunisation of egg allergic children using TIV (25). The programme commenced in Autumn 2013 with all children in the UK aged 2 and 3 years invited to participate. This had a significant impact on referrals to specialist allergy services as immunisation was indicated for a large number of egg-allergic children who would previously not have received seasonal flu vaccine.

STUDY JUSTIFICATION

The intranasal LAIV contains under 240ng of ovalbumin, which is delivered to the nasal mucosa. This amount is in the mid-range in terms of the amount of ovalbumin in parenteral influenza vaccine formulations. Estimates of the paediatric ED₁₀ (amount of protein needed to trigger an allergic reaction in at least 10% of children) is around 20mg – i.e. 10^5 x more than that delivered by the vaccine (28, 29). In a recent study by Clark et al, intranasal challenges were performed in peanut-allergic children using a dose of peanut (10µg) approximately 300 times less than the established ED₁₀ for peanut (approximately 3mg peanut protein)(30). Patients experienced mild symptoms of rhinitis only, with no other organ involvement or evidence of systemic reaction.

During the influenza season 2013/14, the SNIFFLE I study reported no systemic or significant local allergic reactions with 433 doses of trivalent-LAIV administered in 282 egg-allergic children. Eight children experienced possible local allergic symptoms following LAIV, all of which were mild, self-limiting and occurred within 30 minutes of LAIV administration. On the basis of these data, the 95% upper confidence interval for occurrence of a significant allergic reaction to LAIV in egg-allergic children is <1.3%, equivalent to under 1 in 77 doses. The current study will increase the power of this safety calculation, to that which might be viewed as being acceptable to permit future use of LAIV in egg-allergic children in the primary care setting.

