The existing data strongly suggest that few, if any, egg-allergic children will experience significant symptoms following intranasal LAIV administration. In order to achieve a larger sample size, secondary paediatric centres (in addition to tertiary paediatric allergy clinics) will be included, where there is sufficient expertise and experience to safely manage any allergic reaction.

It is proposed that the negligible risk involved to participants is outweighed not only by the protection against influenza infection following vaccination, but also by the demonstration in a larger cohort of patients that LAIV is safe in egg-allergic children. The success of the introduction of annual influenza vaccination to the UK paediatric immunisation schedule depends on the wide availability and uptake of the vaccine. This study will provide the necessary safety data for vaccine use in those children with egg allergy (up to 5% of the total paediatric population for some ages) which will facilitate the planned extensive use of this vaccine as a public health intervention.

STUDY OBJECTIVES

PRIMARY OBJECTIVE

To assess the incidence of immediate allergic reaction to nasal influenza vaccination with LAIV in egg-allergic children

SECONDARY OBJECTIVES

- 1) To assess the incidence of immediate allergic reaction to LAIV in the following subgroups:
 - a) By age group 2-5, 6-11, 12-17 years
 - b) Children with a clinician-assessed history of reaction to egg in the previous 12 months
 - c) Children with evidence of >95% likelihood of egg allergy (defined as a serum specific IgE 6.0 IU/mL or above (31) or skin prick test (SPT) 7mm or above to egg (32, 33) within the past 3 months
 - d) Children with evidence of >95% likelihood of egg allergy (as defined in c) above) within the past 12 months
 - e) children with a previous history of anaphylaxis to egg protein
 - f) children who have reacted previously to airborne traces of egg
 - g) children who have egg allergy but are tolerant of baked egg
 - h) Children who have previously received influenza vaccine
 - i) Presence of physician-diagnosed asthma / recurrent wheeze
- 2) To assess the incidence of delayed symptoms up to 72 hours after nasal influenza vaccination with LAIV in egg-allergic children
- 3) To assess for a change in asthma control (by validated questionnaire) pre and 4 weeks post LAIV immunisation.

STUDY DESIGN

TYPE OF STUDY

- Multicentre, observational study of the safety of LAIV in egg allergic children.

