NUMBER OF SUBJECTS

- 730 children, on the basis of power calculations (see below).

EXPECTED DURATION OF STUDY

- Recruitment to commence 1st September 2014
- Clinical interventions to commence from mid-September 2014 for 5 months.

OUTCOME MEASURES

PRIMARY OUTCOMES:

- Immediate allergic reaction (occurring within 2 hours of administration)

SECONDARY OUTCOMES:

- Adverse events (of non-allergic aetiology) following administration
- Delayed onset allergic reaction (<72 hours following administration)
- Change in asthma control (by a validated questionnaire) pre and post LAIV

STUDY TREATMENT**DESCRIPTION**

Live Attenuated Intranasal Vaccine (Fluenz, Astra Zeneca), as provided for use by the Department of Health as part of the UK National Immunisation Schedule

At the current time, the Department of Health is planning to utilise the LAIV Quadrivalent vaccine (Fluenz Tetra, Astra Zeneca) for the influenza season 2014/15. However, in the event the quadrivalent LAIV is not available, vaccine supply will be with the trivalent LAIV.

DOSAGE AND ROUTE OF ADMINISTRATION

0.2 ml (administered as 0.1 ml per nostril). Immunisation must be carried out by nasal administration.

DOSE MODIFICATION

No dose modification proposed.

PREPARATION AND ADMINISTRATION OF STUDY DRUG

[figure not shown]
[figure not shown]
FLUENZ IS FOR NASAL USE only.

- DO NOT USE WITH A NEEDLE. Do not inject.

[figure not shown]

- FLUENZ is administered as a divided dose in both nostrils.
- After administering half of the dose in one nostril, administer the other half of the dose in the other nostril immediately or shortly thereafter.
- The patient can breathe normally while the vaccine is being administered – there is no need to actively inhale or sniff.
- Refer to the FLUENZ administration diagram (Figure 1) for step-by-step administration instructions.

[figure not shown]
Figure 1 FLUENZ Administration

[figure not shown]
1
Check expiry date
 Product must be used before date on applicator label.

[figure not shown]
2
Prepare the applicator
 Remove rubber tip protector. Do not remove dose-divider clip at the other end of the applicator.

[figure not shown]
3
Position the applicator
 With the patient in an upright position, place the tip just inside the nostril to ensure Fluenz is delivered into the nose.

4
Depress the plunger
 With a single motion, depress plunger as **rapidly as possible** until the dose-divider clip prevents you from going further.

5
Remove dose-divider clip

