Allergic reactions to LAIV will be determined using the World Allergy Organisation (WAO) criteria for allergic reactions to immunotherapy, reproduced below. **For the purpose of this study**, mild symptoms of an allergic reaction (ie. non-anaphylactic symptoms) will be classified as non-serious adverse event, and should be documented on the CRF.

Any symptoms requiring treatment for anaphylaxis (adrenaline, steroids, salbutamol) **will be classified as a SERIOUS ADVERSE REACTION** and will be documented on both the CRF and a SAE form. The local investigator should also make a notification to the MHRA through the MHRA yellow card scheme.

On receipt of CRF / SAE forms, allergic reactions will be further classified by the ISC using World Allergy Organisation (WAO) criteria, which can be mapped to these grades and can be used to inform as to the appropriate NTI-CTCAE grade (Table 3).

Anaphylaxis will be defined as per the case definition and guidelines as described by the Brighton Collaboration Anaphylaxis Working Group (34) (see appendix 1).

WORLD ALLERGY ORGANISATION (WAO) GRADING SYSTEM FOR ALLERGIC REACTIONS TO IMMUNOTHERAPY

Grade 1	Grade 2	Grade 3	Grade 4	Grade 5

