The study coordination centre will notify the MHRA, REC and the Sponsor of all SUSARs occurring during the study according to the following timelines: fatal and life-threatening within 7 days of notification and non-life threatening within 15 days. All investigators will be informed of all SUSARs occurring throughout the study. Local investigators should report any SUSARs and /or SAEs as required by local requirements including the appropriate local Research & Development Office.

SUMMARY AND CONTACT DETAILS FOR REPORTING SAE AND SUSARS

Contact details for reporting SAEs and SUSARs:

[contact], attention [name]

Email: [contact]

STATISTICAL METHODS

SAMPLE SIZE ESTIMATION

Sample size is considered with respect to a historical comparison and also based on the precision around an estimate of 0%.

The SNIFFLE 1 study reported no systemic allergic reactions with 433 doses of LAIV administered to 282 egg-allergic children. On the basis of these data, the 95% upper confidence interval for occurrence of a significant allergic reaction to LAIV in egg-allergic children is <0.85%.

If, in a sample size of 730, there are no systemic or significant local allergic reactions, then this would provide confidence (at the 95% CI) that the true rate of allergic reaction to LAIV in egg-allergic children within the population is no more than 0.5%.

POPULATION TO BE ANALYSED

Children aged 2-17 years old with a physician-diagnosis of egg allergy as defined above.

STATISTICAL ANALYSIS PLAN

The incidence of reactions to LAIV (both immediate and delayed) will be estimated with 95% confidence intervals. Comparison to historical rates will be by Fisher's exact test. For the subgroup analyses, incidence of reactions will be compared between different cohorts (e.g. children with and without prior anaphylaxis to egg protein). Statistical differences will be determined using Fisher's exact test for proportions or using non-parametric tests for graded reactions. Sub-group analyses will be performed using the following criteria:

- Likelihood of clinical egg allergy (<95% and >95% likelihood)
- Severity of egg allergy
- Severe egg allergy – i.e. prior anaphylaxis to egg protein
- Baked egg tolerant
- Previous respiratory reactions to airborne egg
- Presence of physician-diagnosed asthma / recurrent wheeze
- Age: 2-5, 6-11, 12-17 years
- Children who have previously received influenza vaccine

INTERIM ANALYSIS

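### The 0.5% bound that justifies 730 children holds for systemic or significant local reactions only, not for the primary outcome of any immediate allergic reaction

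*Protocol*

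**What the plan says.** **Objective and outcome.** The primary objective is "To assess the incidence of immediate allergic reaction to nasal influenza vaccination with LAIV in egg-allergic children". The primary outcome, under Outcome Measures, is "Immediate allergic reaction (occurring within 2 hours of administration"). Neither sets a severity threshold.

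**What counts as an allergic reaction.** The section on grading of allergic reactions states: "Allergic reactions to LAIV will be determined using the World Allergy Organisation (WAO) criteria for allergic reactions to immunotherapy". In the WAO table reproduced there, grade 1 needs signs in one organ system only, and rhinitis alone qualifies. The same section treats mild, non-anaphylactic symptoms as allergic reactions to be recorded as non-serious events. The note closing Appendix 1 classes local rhinitis and oropharyngeal symptoms as local rather than systemic. It does not say that they stop being allergic reactions.

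**Sample size.** Under Number of Subjects the protocol gives "730 children, on the basis of power calculations (see below"). Sample Size Estimation refers to a historical comparison and to precision around an observed rate of zero. Its condition is "If, in a sample size of 730, there are no systemic or significant local allergic reactions". Its conclusion is that "the true rate of allergic reaction to LAIV in egg-allergic children within the population is no more than 0.5" per cent.

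**Earlier data.** Study Justification reports 433 doses in 282 children and adds: "Eight children experienced possible local allergic symptoms following LAIV, all of which were mild, self-limiting". All eight occurred within 30 minutes of the dose.

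**The concern.** Seeing no events in a subset bounds the rate of that subset, not the rate of the wider class. The condition concerns systemic or significant local reactions, while the conclusion concerns allergic reactions in general, which is what the primary outcome counts. As written, the inference does not follow.

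This matters because the 0.5% sentence is the only precision figure stated for 730 children. Study Justification also presents the trial as tightening the safety bound to a level that might be acceptable for vaccination in primary care. A reader will take 0.5% as the precision to expect for the primary result, and may then be shown a rate of a few per cent with no warning that the two figures describe different events.

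In addition, the protocol does not define a significant local reaction, and the sized event is not among the listed outcomes. The event to which 0.5% does apply therefore has an open boundary.

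**Working it through.** **Inputs.** N = 730 (Number of Subjects). Previous study: 0 systemic or significant local reactions, and 8 children with possible local allergic symptoms, in 282 children and 433 doses (Study Justification).

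**1. Reproduce the plan's figure.** The exact two-sided 95% upper limit for 0 of n is 1 − 0.025^(1/n).
- n = 730: 0.504%, which the protocol rounds to 0.5%.
- n = 433: 0.848% (stated as below 0.85% in Sample Size Estimation).
- n = 282: 1.30% (stated as below 1.3% in Study Justification).

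All three agree, so this is the method in use. A bound of exactly 0.5% needs n = ln(0.025)/ln(0.995) = 735.9, that is 736, so 730 is close enough.

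**2. Rate of the primary outcome suggested by the previous study** (exact Clopper–Pearson 95% CI).
- Per dose: 8/433 = 1.85% (0.80–3.61%), taking one event per affected child.
- Per child: 8/282 = 2.84% (1.23–5.51%).

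Children in that study averaged 433/282 = 1.5 doses. The primary analysis here uses one dose per child, so the per-child rate is the upper end of the range.

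**3. Expected primary events in 730.**
- 730 × 0.01848 = 13.5
- 730 × 0.02837 = 20.7

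**4. Probability of zero primary events**, (1 − p)^730.

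| Assumed rate p | Expected events | P(zero) |
|---|---|---|
| 1.85% | 13.5 | 1.2 × 10⁻⁶ |
| 2.84% | 20.7 | 7.5 × 10⁻¹⁰ |
| 0.80% (lower limit, per dose) | 5.8 | 0.28% |
| 1.23% (lower limit, per child) | 9.0 | 0.01% |

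**5. Precision to expect for the primary outcome** (exact 95% CI).
- 13/730 = 1.78%: 0.95–3.03%
- 21/730 = 2.88%: 1.79–4.36%

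The upper limits are 3.03/0.504 = 6.0 and 4.36/0.504 = 8.7 times the stated bound.

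**6. Bound for the sized event if it is not zero** (exact two-sided 95% upper limit, n = 730).

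| Events | Upper limit |
|---|---|
| 0 | 0.50% |
| 1 | 0.76% |
| 2 | 0.99% |
| 3 | 1.20% |

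**The case against.** The best defence is that the sentence is openly conditional and is introduced as precision around zero. The protocol never predicts that no child will have any reaction, and Study Justification reports the eight mild cases beside the zero-event bound, so a careful reader can work out which event is meant. This lessens the fault but does not remove it. The conclusion still drops the restriction, and no precision is given for the outcome named as primary.

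A second defence is that the 1.8–2.8% range is uncertain, and this stands. The eight cases are called possible. The Background reports nasal symptoms in 12% on day 0–1 after nasal saline placebo, so some may not have been allergic. The earlier cohort had a likelihood of egg allergy above 95%, whereas this trial accepts any physician diagnosis. The range is therefore a planning assumption. It would have to be far too high for zero primary events to become plausible, as step 4 shows.

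A reader might also infer that the 0.5% claim will rest on a subset picked after the results are known. The documents do not support that. The subset is named in advance in Sample Size Estimation and in Study Justification, the internal study committee (ISC) is to classify reactions by WAO grade, and anaphylaxis follows the Brighton definition. Only the threshold for a significant local reaction is left open.

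**Conclusion.** The 0.5% bound is correctly computed but attached to the wrong event. It applies to systemic or significant local reactions, and only if none occurs; it is not the precision of the primary outcome. If 1.8–2.8% of children react, the primary result would be about 13 to 21 events with an upper 95% limit of about 3.0–4.4%. This assumes that the eight possible reactions are a fair guide to the new cohort. The weaker conclusion, that zero primary events is very unlikely, needs only a true rate at or above the lower confidence limits of the earlier data.

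Two further inferences are not supported. The first is that 730 is too few: the planned analysis estimates incidence with a 95% confidence interval whatever the count, and an interval of roughly ±1.0 to ±1.3 percentage points has not been shown to be inadequate. The second is that the primary outcome should be replaced by a severe one. That is a debatable design change. A simple cut at WAO grade 2 would also lose isolated generalised urticaria, generalised pruritus and non-laryngeal angioedema, which are grade 1 but are not set aside by the Appendix 1 note.

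**What to change.** Keep the primary outcome and make these changes:

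1. **Sample Size Estimation.** Restrict the 0.5% sentence to systemic or significant local allergic reactions in its conclusion as well as its condition. Give the upper bounds for 0, 1, 2 and 3 events from step 6.
2. **Definition.** Define that event before any data are seen, from the Brighton and WAO criteria already in the protocol and the Appendix 1 note. Since the note sets aside only local rhinitis and oropharyngeal symptoms, generalised skin reactions of WAO grade 1 should still count. State what makes a local reaction significant.
3. **Outcome Measures.** List the event as a named outcome, classified by the ISC.
4. **Precision of the primary outcome.** State it separately: an upper 95% limit of about 3.0–4.4% if 1.8–2.8% react, noting that these rates come from possible reactions in a differently selected cohort.

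The cost is wording in two sections and one definition, with no extra children or data. The downside is that the headline figure becomes narrower in scope and less favourable.

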3. Patients enrolled in Northern Ireland will be funded through locally-held Public Health funds

INTRODUCTION AND BACKGROUND

BACKGROUND INFORMATION

Egg allergy is one of the most common food allergies in childhood with an estimated prevalence of at least 2% in preschool children (1). Natural tolerance is acquired during childhood so that only about 0.1% of adults have egg allergy (2)

Influenza vaccines contain egg protein as the vaccine virus is cultured in hen’s eggs. Individuals who have egg allergy may be at increased risk of reaction to influenza vaccines. In recent years, inactivated influenza vaccines that are egg-free or have a very low ovalbumin content have become available. Table 1 lists the vaccines currently available within the UK. Observational studies have confirmed the safety of the parenteral influenza vaccine in egg-allergic children, including those with a history of previous anaphylaxis to egg protein (3, 4). A recent literature review reported safety data for administration of the parenteral influenza vaccine in over 4000 children with egg allergy (over 3-fold greater than the available data on the use of MMR in egg-allergic children) concluded that “there is now robust evidence that egg-allergic patients, even those with severe allergy, can be safely vaccinated against influenza” (3, 4). These observations only apply to inactivated Trivalent Influenza Vaccine (TIV) delivered by intramuscular injection, and have led to a relaxation of contraindications in the last few years (5, 6). With increased safety data it has become routine to immunise low-risk, egg-allergic children in primary care. It is likely that this will soon extend to children with anaphylaxis to egg in a similar way to the relaxation of the rules surrounding MMR and egg allergy (7).

Supplier	Product	Vaccine type	Age indication	Ovalbumin content (ng per dose)
Abbott Healthcare	Influvac	Inactivated	> 6 months	100
	Imuvac	Inactivated	> 6 months	100
Janssen-Cilag	Viroflu	Inactivated	> 6 months (caution in <5yrs)	<50
	Inflexal V	Inactivated	> 6 months (caution in <5yrs)	<50
GSK	Fluarix	Inactivated	> 6 months	<50
Masta	Imuvac	Inactivated	> 6 months	100
	Influvac	Inactivated	> 6 months	100
	Split virion BP	Inactivated	> 6 months	<50
Novartis	Agrippal	Inactivated	> 6 months	<200
	Fluvirin	Inactivated	> 4 years	<1000
	Optaflu	Inactivated	> 18 years	None
Pfizer	Influenza vaccine	Inactivated	> 5 years	<1000
	Enzira	Inactivated	> 5 years	<1000

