In the United States, LAIV was initially approved for use in individuals aged 5-49 years in 2003, which was extended to individuals aged 2-49 years in 2007 (19). It has been given to several million people since that time (20). The vaccine has proven to be safe and efficacious, and equivalent to TIV in terms of its safety profile (18, 21-26). There have been no reports of accidental administration in children with egg allergy during this time, although it is likely to have occurred. There are only 7 reported cases of anaphylaxis as an adverse event following administration of LAIV (20, 25). Of these only 5 were thought to be causally related to vaccine administration and none were related to egg allergy (20). The estimated rate of anaphylaxis following LAIV administration is 1 case in 20,000 to 1,000,000 doses (20).

There are currently no published data on the safety of LAIV in egg-allergic children, thus its use in this population (under the terms of its license by regulatory authorities) has been contraindicated. However, a recent safety surveillance study (The SNIFFLE I study) commissioned by Public Health England on behalf of the UK Department of Health assessed the safety of trivalent-LAIV in children with >95% likelihood of clinical egg allergy. A total of 433 doses were administered in 282 children, with no systemic allergic or anaphylactic reactions observed (manuscript currently in submission).

At the current time, the Department of Health is planning to provide quadrivalent LAIV for use as part of the UK National Immunisation Programme for the 2014/15 influenza season. This is because the quadrivalent vaccine includes four rather than three influenza strains, which results in improved immunity (27). The manufacturer has stated that the egg protein content of the two different vaccines (trivalent vs quadrivalent) is the same.

RESEARCH QUESTION

To assess the safety of LAIV (Fluenz[®], Astra Zeneca) in children with a physician diagnosis of egg allergy, in order to determine the safety of immunisation of egg-allergic children using LAIV in primary care.

RATIONALE FOR CURRENT STUDY

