 - E0 – avoids all foods containing egg in any form
 - E1 – tolerates egg in baked foods (cakes, biscuits) but not other forms
 - E2 – able to eat lightly cooked egg (e.g. scrambled egg, boiled egg) but reacts to raw egg in uncooked cake mixtures, fresh mayonnaise, ice cream etc.
3. Written informed consent from parent/guardian (or the patient themselves from age 16 years), with assent from children aged 8 years and above wherever possible.

EXCLUSION CRITERIA

1. **Clinical resolution of egg allergy**
2. **Contraindications to LAIV** (notwithstanding allergy to egg protein), which include:
 - a. Hypersensitivity to the active ingredients, gelatin or gentamicin (a possible trace residue)
 - b. Previous systemic allergic reaction to LAIV
 - c. Previous allergic reaction to an influenza vaccine (not LAIV) is a relative contra-indication, which must be discussed with the site PI to confirm patient suitability
 - d. Children/adolescents who are clinically immunodeficient due to conditions or immunosuppressive therapy such as: acute and chronic leukaemias; lymphoma; symptomatic HIV infection; cellular immune deficiencies; and high-dose corticosteroids*.

***High-dose steroids** is defined as a treatment course for at least one month, equivalent to a dose of prednisolone at 20mg or more per day (any age); or for children under 20kg, a dose of 1mg/kg/day or more.

NB: LAIV is not contraindicated for use in individuals with asymptomatic HIV infection; or individuals who are receiving topical/inhaled/low-dose oral systemic corticosteroids or those receiving corticosteroids as replacement therapy, e.g. for adrenal insufficiency.

- e. Children and adolescents younger than 18 years of age receiving salicylate therapy because of the association of Reye's syndrome with salicylates and wild-type influenza infection.

3. **Contraindication to vaccination on that occasion**, e.g. due to child being acutely unwell:

- a. Febrile $\geq 38.0^{\circ}\text{C}$ in last 72 hours
- b. Acute wheeze in last 72 hours requiring treatment beyond that normally prescribed for regular use by the child's treating healthcare professional
- c. Recent admission to hospital in last 2 weeks for acute asthma
- d. Current oral steroid for asthma exacerbation or course completed within last 2 weeks
- e. Recent use (within last 96 hours) of an antihistamine

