Existing data relating to skin prick testing to egg (where performed in routine clinical practice, according to BSACI guidelines (http://www.bsaci.org/Guidelines/Skin_Prick_Testing.pdf) and/or allergy blood tests (serum specific IgE to egg) will be collected from medical records, where available, to confirm sensitisation to egg.

No allergy testing will be performed as part of this protocol.

CLINICAL OBSERVATION / MONITORING OF PATIENTS BY CLINICAL STAFF

Patients will have baseline observations (temperature, heart rate, respiratory rate, oxygen saturations) performed prior to LAIV administration, with clinical respiratory and dermatological assessment at the same time.

Patients will be observed for at least 30 minutes after administration of LAIV, for symptoms of local or systemic allergic reaction. Symptoms (Total Nasal Symptom Score, TNSS) will be recorded at 10 and 30 minutes after vaccine administration, as follows:

Total nasal symptom score (TNSS)	
Rhinorrhoea	FOR EACH SYMPTOM, SCORE: 0 = no sign/symptom evident
Nasal congestion	1 = mild symptoms (sign/symptom clearly present, but minimal awareness; easily tolerated) 2 = moderate symptoms (definite awareness of sign/symptom that is bothersome but tolerable)
Nasal itch	3 = severe symptoms (sign/symptom that is hard to tolerate; causes interference with activities of daily living)
Sneezing	

[figure not shown]
US Department of Health and Human Services Food and Drug Administration, Allergic Rhinitis: Clinical Development Programs for Drug Products; 2000.
<http://www.fda.gov/downloads/Drugs/GuidanceComplianceRegulatoryInformation/Guidances/ucm071293.pdf>

Children will be observed in safe environment with appropriate clinical supervision and access to paediatric resuscitation facilities and trained staff, in the event of an anaphylactic reaction.

In the SNIFFLE study (2013/14 season), 8 children experienced possible local allergic symptoms following LAIV, all of which were mild and self-limiting. Symptoms commenced within 30 minutes of LAIV administration in all cases. Children will therefore be observed for 30 minutes, and if no symptoms are observed, discharged from the vaccine clinic. However, further clinical observations will be collected in the event of a clinical reaction, as per local policy.

TREATMENT OF ALLERGIC REACTIONS

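### The comparison with SNIFFLE 1 sets all physician-diagnosed children against a cohort selected for >95% likelihood of egg allergy, so a lower rate of local or all immediate reactions may reflect case-mix

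*Protocol*

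**What the plan says.** The Background section says that SNIFFLE 1 "assessed the safety of trivalent-LAIV in children with >95% likelihood of clinical egg allergy". The Sample Size Estimation section takes it as the historical reference: "The SNIFFLE 1 study reported no systemic allergic reactions with 433 doses of LAIV administered to 282 egg-allergic children", with an upper limit of <0.85%. It then states that zero reactions in 730 children would support a limit of 0.5%. The Study Justification says: "The current study will increase the power of this safety calculation".

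The new study enters children on a physician diagnosis plus current avoidance of egg in category E0, E1 or E2. E2 covers children "able to eat lightly cooked egg (e.g. scrambled egg, boiled egg) but reacts to raw egg". Clinical resolution of the allergy is an exclusion. The population to be analysed is: "Children aged 2-17 years old with a physician-diagnosis of egg allergy as defined above". The next section says "Comparison to historical rates will be by" Fisher's exact test, without limiting that comparison to any part of the cohort.

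The >95% group is defined in secondary objectives 1c and 1d: specific IgE of at least 6.0 IU/mL, or a skin prick test of at least 7 mm, within 3 or 12 months. Its incidence is a secondary objective, and a <95% v >95% contrast is on the subgroup list. Test results come from existing records where available: "No allergy testing will be performed as part of this protocol".

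**The concern.** The historical group was selected on a high probability of true allergy. The new cohort is not. If children below the >95% threshold react less often, the whole-cohort rate falls even though the vaccine is just as safe in the kind of child SNIFFLE 1 studied. An unrestricted Fisher test cannot separate these explanations. The planned subgroup contrast does not help, because it compares children within SNIFFLE 2 and is not tied to the historical test.

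This matters because the study is meant to support vaccination in primary care. The primary outcome is any immediate allergic reaction, and grade 1 on the adopted grading scale includes rhinitis. Mild local events can therefore enter the comparison. Separately, a reader who sees 0.5% beside <0.85% may take it as tighter evidence about the same children.

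**Working it through.** **Inputs from the protocol.** SNIFFLE 1: 0 systemic reactions in 282 children (433 doses), and 8 children with possible mild local symptoms. SNIFFLE 2: 730 children. **Not in the protocol:** the share *f* of the 730 who meet the >95% definition (assumed 30% to 70%), and the reaction rate in the other children.

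**1. The plan's own limits.** With zero events, the exact two-sided 95% upper limit is U(n) = 1 − 0.025^(1/n).
- U(730) = 0.504% (stated 0.5%; exactly 0.5% needs n = ln 0.025 / ln 0.995 = 735.9, so 736)
- U(433) = 0.848% (stated <0.85%, per dose)
- U(282) = 1.300% (stated <1.3%; this uses the number of children)

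All three reproduce. Setting 0.5% against 0.85% also puts a per-child figure beside a per-dose one. The per-child pair is 0.50% v 1.30%.

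**2. The limit for children like those in SNIFFLE 1.** Put n = 730*f* into the same formula:

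| Assumed share *f* | n | Upper limit, zero events |
|---|---|---|
| 70% | 511 | 0.72% |
| 50% | 365 | 1.01% |
| 40% | 292 | 1.26% |
| 30% | 219 | 1.67% |

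Below 282/730 = 38.6%, SNIFFLE 2 alone gives this group a wider per-child limit than SNIFFLE 1 did.

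**3. Systemic reactions.** 0/730 v 0/282 gives p = 1.0, and any event in SNIFFLE 2 makes its rate the higher one. Fisher's test cannot favour the new cohort here.

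**4. Local reactions.** The SNIFFLE 1 rate is 8/282 = 2.84%. Against 8/282, 7/730 gives p = 0.039 and 8/730 gives p = 0.086, so seven or fewer events is significantly lower.

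Let the >95% children keep the 2.84% rate and let the others have *r* times it. The count is then Bin(730*f*, 8/282) + Bin(730(1−*f*), *r*·8/282), with mean 730 × (8/282) × [*f* + (1−*f*)*r*]. The chance of seven or fewer, holding SNIFFLE 1 at 8/282, is:

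| *f* | Mean, *r* = 0 | Chance | Mean, *r* = 0.5 | Chance |
|---|---|---|---|---|
| 70% | 14.5 | 2% | 17.6 | 0.3% |
| 50% | 10.4 | 19% | 15.5 | 1.2% |
| 40% | 8.3 | 41% | 14.5 | 2.3% |
| 30% | 6.2 | 72% | 13.5 | 4.1% |

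At *r* = 0.75 the chance is 0.5% or less at each of these shares.

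**5. Two sensitivities.**
- If the SNIFFLE 1 count also varies as Bin(282, 8/282), the chance at *f* = 50% is 29% for *r* = 0 and 9% for *r* = 0.5. It is 2.3% when the populations match.
- Per dose, 8/433 moves the cut-off to 3/730 (p = 0.024). With *r* = 0 the chances are about 9%, 21% and 42% at shares of 50%, 40% and 30%.

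**The case against.** The strongest reply is that the broad cohort is the intended one. Primary care will identify these children by physician diagnosis, the protocol names that population directly after the 0.5% statement, and the limit is valid for it. This stands. A reader might infer that the 0.5% is wrong or mislabelled; the documents do not support that.

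Second, the large false-positive chances need a zero rate in every child outside the >95% group. The Background section reports nasal symptoms in about 12% on day 0–1 after nasal saline placebo, so some background attribution is likely whatever the egg status. This also stands, and it is why the *r* = 0 figures are an extreme.

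Third, incidence in children with a recent reaction and in the >95% group is already planned (objectives 1b to 1d), with confidence intervals. SNIFFLE 1 recipients are also re-invited, which would tend to raise the share. Both are true, and further event-free >95% children could only add to the evidence. Neither ties the historical test to the matching children.

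Two further inferences are tempting. One is that children who avoid all egg may have outgrown the allergy unnoticed. The Background does say "Natural tolerance is acquired during childhood so that only about 0.1% of adults have egg allergy", but clinical resolution is excluded and nothing shows how often it would be missed. The other is that E1 and E2 children are new to this study; the protocol does not say that SNIFFLE 1 left them out.

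Finally, details of a test can be left to a statistical analysis plan. Here, however, the protocol itself fixes the population, the comparator and the test.

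**Conclusion.** The mismatch is in the text and should be corrected. As written, a lower rate of local or all immediate reactions than in SNIFFLE 1 cannot be read as better vaccine safety, and 0.5% should not be read as an improvement on <0.85% for the same kind of child.

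The size is uncertain. The subgroup limits of 0.72% to 1.67% rest on an assumed share of 70% to 30% and on zero events. The chance of a false significant result on local reactions, with SNIFFLE 1 held at 8/282, runs from about 1–4% (other children at half the SNIFFLE 1 rate) to 19–72% (other children at zero) for shares of 50% to 30%. The upper end should not be quoted alone. The problem does not extend to Fisher's test on systemic reactions, and the overall 0.5% limit remains correct for physician-diagnosed children.

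**What to change.** In the Statistical Analysis Plan section:

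- Make the comparison with SNIFFLE 1 in the SNIFFLE 2 children who meet the >95% likelihood definition (objective 1d, test within 12 months), per child and with the same reaction definition in both studies. The protocol does not give SNIFFLE 1's test criteria, so confirm that they match objective 1d.
- Report any whole-cohort comparison with SNIFFLE 1 as descriptive only.
- Give the >95% group's exact upper limit, at the number achieved, next to the overall limit.
- State how many children have no usable test result.

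A first-dose-only match cannot be specified from this protocol, because SNIFFLE 1 events are not split by dose.

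The change is to wording and analysis only. The Data Collection section already lists recent skin test and specific IgE results. The costs are a smaller n, a less favourable limit for the >95% group, and the loss from the historical comparison of children without a recorded test, which may itself be selective.
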